8.4.8. Unscheduled visits

An unscheduled visit is defined as a visit that occurs after the MRI Scan Visit where the subject is seen in clinic due to an ADE or SADE associated with the study lead(s) and study ICD/ CRT-D. Where possible, perform a device interrogation for the applicable lead(s) to obtain:

- In-clinic bipolar and unipolar* capture threshold at a pulse width of 0.5 ms.
- In-clinic bipolar sensing amplitude. Either the incremental or the automatic (in-clinic, programmer based) method may be used to measure the sensing threshold.
- In-clinic atrial and ventricular bipolar and unipolar* lead impedance

**NOTE: Unipolar and bipolar configurations should be collected for LV leads*

8.4.9. Data submission

Once testing has been performed, complete and submit the appropriate forms to Abbott. Refer to **Table 4**. It is recommended that the following device printouts and measurements be maintained at the site:

- FastPath Summary
- Test Results with freezes, Include Battery & Leads
- Wrap-up Overview with full parameters

8.4.10. Non-Study MRI Scans

A non-study MRI scan is defined as an MRI scan occurring at any time following the study MRI scan to the conclusion of the subject's participation in the study. Non-study MRI scans should be performed per each center's standard of care. A non-study scan may be performed 30 minutes after the study scan on the same day, if the Investigator and Subject choose to have one performed.

For non-study MRI scans performed at the study center, the same safety data collection and safety precautions outlined at the MRI Scan Visit should be followed. However, if procedures or data are not followed or collected as presented on the non-study MRI Case report form during a non-study MRI scan, it will not be considered a protocol deviation.

MRI Scan Analysis

The MRI scan should be reviewed for obvious abnormalities by a radiologist and reported to the subject's physician (per standard of care by the facility performing the MRI scan).

The following data should be collected and reported to Abbott for non-study MRI scans.

- Date of scan
- Type of scan performed

- Documentation of any Adverse Device Effects
- Device diagnostics, if available
- MRI Scan report, if available
- Fast Path Summary, if available

9. Standards for device use

The product labeling for the study devices, instructions for use and packaging are kept under a separate cover and will be provided to the NMPA in the application.

10. Monitoring plan

Sponsor and/or designee will monitor the clinical study over its duration according to the CIP-specific monitoring plan which will include the planned extent of source data verification.

Prior to initiating any procedure, the Sponsor monitor (or delegate) will ensure that the following criteria are met:

- The investigator understands and accepts the obligation to conduct the clinical study according to the CIP and applicable regulations and has signed the Clinical Trial Agreement.
- The Investigator and his/her staff should have sufficient time and facilities to conduct the clinical study and should have access to an adequate number of appropriate subjects to conduct the clinical study.
- Source documentation (including original medical records) must be available to substantiate proper informed consent procedures, adherence to CIP procedures, adequate reporting and follow-up of adverse events, accuracy of data collected on case report forms, and device information.
- The Investigator/site will permit access to such records. A monitoring visit sign-in log will be maintained at the site. The Investigator will agree to dedicate an adequate amount of time to the monitoring process. The Investigator and/or research coordinator will be available for monitoring visits. It is expected that the Investigator will provide the monitor with a suitable working environment for review of clinical study-related documents.

11. Statistical considerations

This study is an observational study to meet the requirements for device approval by the NMPA. There is no endpoint hypotheses testing planned in this study. The endpoints, demographics, safety and device data will be summarized using descriptive statistics as outlined in the Statistical Analysis Plan (SAP).

Any major changes to the SAP will be documented in an amendment to the SAP. Less significant changes to the planned analyses will be documented in the final report(s).

12. Data management

Study data will be handled according to China Device GCP (Order 25). The Leading PI and his/her associated organization (leading Unit) will be responsible for compiling and submitting all required reports to governmental agencies.

Before the submission, Leading PI and his/her associated organization (leading Unit) should allow sponsor to have a copy of the above reports for reviewing and providing comments for Leading PI and his/her associated organization consideration.

Data will be analyzed by the Leading PI and his/her associated organization (leading Unit) and/or its affiliates. The Leading PI and his/her associated organization (leading Unit)'s also agree that data may be transferred to the Sponsor's locations worldwide and/or any other worldwide regulatory authority in support of a market-approval application.

13. Quality control of clinical study

13.1. Quality assurance audits and regulatory inspections

The investigator and/or delegate should contact the Sponsor immediately upon notification of a regulatory authority inspection at the site. A monitor or designee will assist the investigator and/or delegate in preparing for the audit. The Sponsor may perform quality assurance audits, as required.

The investigator/institution will permit direct access to source data/documents for the purpose of performing clinical study-related monitoring, audits, IRB/EC review and regulatory inspections.

Subjects providing informed consent are agreeing to allow clinical study monitors or regulatory authorities to review, in confidence, any records identifying the subjects in this clinical study. This information may be shared with regulatory agencies; however, Sponsor undertakes not to otherwise release the subject's personal and private information.

13.2. Repeated and serious non-compliance

In the event of repeated non-compliance or a one-time serious non-compliance, as determined by the Sponsor, a monitor or designee will attempt to secure compliance by one or more of the following actions:

- Visiting the investigator,
- Contacting the investigator by telephone,

- Contacting the investigator in writing,
- Retraining of the investigator.

If an investigator is found to be repeatedly non-compliant with the signed agreement, the CIP or any other conditions of the clinical study, the Sponsor will either secure compliance or, at its sole discretion, terminate the investigator's participation in the clinical study. In case of termination, the Sponsor will inform the responsible regulatory authority, as required, and ensure that the IRB/EC is notified, either by the Principal Investigator or by the Sponsor.

13.3. Complaints

During the study, the investigator will be responsible for reporting all complaints. A complaint is defined as any written, electronic or oral communication that alleges deficiencies related to the identity, quality, durability, reliability, safety, effectiveness or performance of a device after it is released for distribution.

If the complaint does not involve a reportable AE as defined in this protocol, the investigator must notify the Post Market Surveillance Department by submitting the information on the device via email to [contact] or by phone toll free: [name] as soon as possible after becoming aware of the complaint. This information will not be collected on a CRF for the study.

If the complaint involves a reportable AE as defined in this protocol, the investigator must complete an AE CRF, including the information on the complaint and submit to the Sponsor as soon as possible.

13.4. Traceability of Documents and Data

The investigator will ensure accuracy, completeness legibility and timeliness of the data reported to the Sponsor on the CRFs and in all required reports.

13.5. Recording Data

The CRF will be reviewed by the authorized site personnel. An appropriate comment will be provided to explain changes to data reported on the CRF.

14. Ethical issues and informed consent of clinical study

14.1. Ethical considerations

This clinical study will be conducted in accordance with this Clinical Investigation Plan, the Declaration of Helsinki and the Good Clinical Practice (GCP) guidelines of the China National Medical Products Administration (NMPA) Order No.25. The most stringent

[REDACTED]

requirements, guidelines or regulations must always be followed. The conduct of the clinical study will be approved by the appropriate Ethics Committee (EC) of the respective clinical site and as specified by local regulations.

The investigator will not start enrolling subjects or requesting informed consent from any subject prior to obtaining IRB/EC approval and relevant Regulatory Authority approval, if applicable, and authorization from the Sponsor in writing for the clinical study. If additional requirements are imposed by the IRB/EC or relevant Regulatory Authority, those requirements will be followed. If any action is taken by an IRB/EC or a relevant Regulatory Authority with respect to the clinical study, that information will be forwarded to the Sponsor.

14.2. Description of the Methods that will be used to Address Potentially Confounding Factors in the Clinical Study Design

The effectiveness endpoints are change in bipolar ventricular capture and sensing threshold from pre-MRI scan to 1 Month Post Scan for the study lead(s) implanted with the study ICD/ CRT-D. Each subject therefore acts as his/her own control. Therefore, there is no concern for confounding factors for the effectiveness endpoint

14.3. Any Known or Foreseeable Factors that May Compromise the Outcome of the Clinical Study or the Interpretation of the Results

There are no foreseeable factors that may compromise the outcome of the clinical study or the interpretation of the results.

14.4. Approval of study protocol

The lead Investigator and the Sponsor will give approval for this protocol in collaboration with the NMPA. The protocol will be submitted to the study site's research governing bodies for approval and approved before any study activities occur.

14.5. Informed consent process and informed consent form

The Investigator or his/her authorized designee will conduct the Informed Consent process, as required by applicable regulations and the center's IRB/EC. This process will include a verbal discussion with the subject on all aspects of the clinical study that are

relevant to the subject's decision to participate, such as details of clinical study procedures, anticipated benefits, and potential risks of clinical study participation. Subjects must be informed about their right to withdraw from the clinical study at any time and for any reason without sanction, penalty or loss of benefits to which the subject is otherwise entitled. Withdrawal from the clinical study will not jeopardize their future medical care or relationship with the investigator.

During the discussion, the Principal Investigator or his/her authorized designee will avoid any improper influence on the subject and will respect subject's legal rights. The subject shall be provided with the Informed Consent form written in a language that is understandable to the subject and has been approved by the center's IRB/EC. The subject shall have adequate time to review, ask questions and consider participation. The Principal Investigator or his/her authorized designee will make efforts to ensure that the subject understands the information provided. If the subject agrees to participate, the Informed Consent form must be signed and dated by the subject and thereafter by the person obtaining the consent prior to any clinical study-specific procedures. The signed original will be filed in the subject's hospital or research charts, and a copy will be provided to the subject.

Failure to obtain informed consent from a subject prior to clinical investigation enrollment should be reported to Sponsor within 5 working days and to the reviewing center's IRB/EC according to the IRB's/ EC's reporting requirements.

If, during the clinical investigation, new information becomes available that can significantly affect a subject's future health and medical care, the Principal Investigator or his/her authorized designee will provide this information to the subject. If relevant, the subject will be asked to confirm their continuing informed consent in writing.

14.6. Criteria and Procedures for Subject Withdrawal

Each enrolled subject shall remain in the clinical study until completion of the required follow-up period; however, a subject's participation in any clinical study is voluntary and the subject has the right to withdraw at any time without penalty or loss of benefit.

Conceivable reasons for discontinuation may include, but not be limited to, the following:

- Subject death
- Subject voluntary withdrawal
- Subject lost-to follow-up as described below
- Subject's follow-up is terminated according to Section **23.1**.

The Sponsor must be notified of the reason(s) for subject discontinuation. The site will provide this information to the Sponsor. Investigators must also report this to their respective IRB/EC as defined by their institution's procedure(s).

No additional follow-up will be required or data recorded from subjects once withdrawn from the clinical study, except for the status (deceased/alive).

However, if a subject withdraws from the study due to problems related to the safety or performance of the device under investigation, the investigator shall ask for the subject's permission to follow his/her status/condition outside of the clinical study.

In case of subject withdrawal, the site should make attempts to schedule the subject for a final clinical study visit. At this final follow-up visit, the subject will undergo the following assessments:

- Device assessment including:
 - Fast Path Summary
 - Test results with Freezes, include battery and leads
 - Wrap-up overview with full parameters
 - Device MRI summary report (if performed)

Lost-to-Follow-up

If the subject misses two consecutive scheduled follow-up time points and the attempts at contacting the subject detailed below are unsuccessful, then the subject is considered lost-to-follow-up. Site personnel shall make all reasonable efforts to locate and communicate with the subject (and document these efforts in the source documents), including the following, at each contact time point:

- A minimum of two telephone calls on different days over the specified follow-up windows to contact the subject should be recorded in the source documentation, including date, time and initials of site personnel trying to make contact.
- If these attempts are unsuccessful, a letter (certified if applicable) should be sent to the subject.
- If a subject misses one or more non-consecutive follow-up contact time points, it will be considered a missed visit. The subject may then return for subsequent visits. If the subject misses two consecutive time points and the above-mentioned attempts at communicating with the subject are unsuccessful, the subject will be considered lost-to-follow-up.

Note: Telephone contact with General Practitioner, non-clinical investigation cardiologist or relative without the presence of the subject or indirect documentation obtained via discharge letters will not be considered as subject contact.

15. Risks and benefits

The risk analysis included an objective review of published and available unpublished medical and scientific data. The sections below provide an overview of residual risks identified in the risk management report and anticipated benefits of the medical device.

The additional tests and assessments required by the clinical study were analyzed for additional risks and are incorporated in the sections below.

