8.4.4.7. One (1) month post scan visit

8.4.4.7.1. Testing

Interrogate the ICD/ CRT-D and obtain electrical lead measurements.

- In-clinic bipolar and unipolar* capture threshold at a pulse width of 0.5 ms. Either the manual decrement or automatic (in-clinic, programmer based) method may be used to obtain the capture threshold. If a significant rise in pacing threshold ([contact] or greater) from pre-MRI scan to one-month post MRI scan has occurred, then complete an AE form.
- In-clinic bipolar sensing amplitude. Either the incremental or the automatic (in-clinic, programmer based) method may be used to obtain the sensing threshold.
- In-clinic atrial and ventricular bipolar and unipolar* lead impedance
- Evaluate the subject for ADE and SADE and submit an AE CRF- if applicable.

***NOTE:** *Unipolar and bipolar configurations should be collected for LV leads*

NOTE: *RV capture thresholds are not required to be obtained if a high ventricular rate (e.g. 110bpm) is present. If available, sites should use the automatically obtained pacing capture threshold from the most recent archival data as a substitute for the in-clinic capture threshold. RV sensing measurements are not required if the subject's intrinsic rate is established to be ≤ 30 beats per minute.*

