8.4.6. Complete system explants

If the subject has the entire study ICD/ CRT-D system removed at any time during the study, and the subject will not receive a replacement study ICD/ CRT-D system, withdraw the subject from the study. Complete a Product Out of Service CRF and submit through EDC. A System Revision CRF is not required to be submitted.

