8.4.7.2. Revisions after the MRI scan

If a system revision occurs after the MRI scan, then the subject will remain in the study until the subject completes the 1 Month Post Scan visit.

Any explanted devices or leads (including damaged leads, lead segments and lead fragments) should be returned to Abbott promptly for analysis. Document any change to the status of the lead and device (e.g. capped, removed) on the Product Out of Service CRF. Refer to

Table 9: System Revisions Scenarios After MRI Scan below to determine what actions need to be performed.

TABLE 8: SYSTEM REVISIONS SCENARIOS PRIOR TO MRI SCAN

System Revisions that occur prior to MRI Scan	Action	Data Submission

Revisions where the study ICD/ CRT-D system is still implanted:
 
 • Study lead(s) or the ICD/ CRT-D is repositioned or replaced, AND • The study ICD/ CRT-D and study lead(s) are still implanted, AND • No other non-MRI compatible material has been implanted 	
Obtain (if possible):
 
 • In-clinic bipolar and unipolar* capture threshold at a pulse width of 0.5 ms. for the applicable lead(s). Either the manual decrement or automatic (in-clinic, programmer based) method may be used to obtain the capture threshold. • In-clinic bipolar sensing amplitude for the applicable lead(s). Either the incremental or the automatic (in-clinic, programmer based) method may be used to obtain the sensing threshold. • In clinic atrial and ventricular bipolar and unipolar* lead impedance for the applicable lead • Retain the subject in the study. If the MRI scan visit has not occurred yet, then wait at least 45 days from the successful revision before completing the MRI scan visit. If the MRI scan visit has occurred, then follow the subject through the 1 Month Post Scan visit. 
*NOTE: Unipolar and bipolar configurations should be collected for LV leads
	
Complete and submit the appropriate forms to Abbott. Refer to Table 4. It is recommended that the following device printouts and measurements be maintained at the site.
 
 • FastPath Summary • Test Results with Freezes, Include Battery & Leads • Wrap-up Overview with full parameters

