
Revisions where the study ICD/ CRT-D system is still implanted
 
 The study ICD/ CRT-D and study lead(s) are still implanted, BUT A non-MRI compatible material(s) or device(s) has been implanted 
OR
 
Revisions where the study ICD/ CRT-D system is still implanted
 
 Study ICD/ CRT-D and study lead(s) is repositioned or replaced, AND The study ICD/ CRT-D and study lead(s) are still implanted, AND No other non-MRI compatible material has been implanted 	
Obtain (if possible):
 
 In-clinic bipolar and unipolar* capture threshold at a pulse width of 0.5 ms. for the applicable lead(s). Either the manual decrement or automatic (in-clinic, programmer based) method may be used to obtain the capture threshold. In-clinic bipolar sensing amplitude for the applicable lead(s). Either the incremental or the automatic (in-clinic, programmer based) method may be used to obtain the sensing threshold. In clinic bipolar and unipolar* lead pacing impedance for the applicable lead(s) Continue to follow the patient until the subject completes the 1 Month Post scan visit. 
*NOTE: Unipolar and bipolar configurations should be collected for LV leads
	Once required testing has been performed, complete and submit the appropriate forms to Abbott. Refer to Table 4

Revisions where the study lead(s) is not retained
 
 Study lead(s) is replaced with another lead, AND The study ICD/ CRT-D is still implanted, AND 	The subject will be withdrawn from the study.	
Document consenting information (name of the study, date of consent and inclusion/exclusion) in the subject's medical and/or study records.
 
Submit the Pre-MRI CRF, MRI CRF, System Revision CRF and Withdrawal CRF. Submit

System Revisions that occur after the MRI Scan	Action	Data Submission

 • A non-MRI compatible material(s) or device(s) has been implanted 		
Deviation, Product Out of Service, Adverse Event CRFs if applicable.
 
It is recommended that the following device printouts and measurements be maintained at the site.
 
 • FastPath Summary • Test Results with freezes, Include Battery & Leads • Wrap-up Overview with full parameters

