3.2 Adverse Events

CEC adjudicated ADE, SADE, USADE data will be summarized in terms of the number of events, the number of subjects with event(s), and the percentage of subjects with event(s). Subjects who die or withdraw before 1-month post-MRI scan will be included in the denominator, and their last known status of event will be included in the numerator.

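### After a post-scan withdrawal the plan stops recording adverse events, but the SAP still counts the subject as followed, so ADE, SADE and USADE percentages can read too low

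*Combined protocol and SAP*

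**What the plan says.** **Recording after withdrawal.** CIP 14.6: "No additional follow-up will be required or data recorded from subjects once withdrawn from the clinical study, except for the status (deceased/alive"). CIP 8.3.2 also ends safety surveillance and reporting at withdrawal.

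**The final visit.** CIP 14.6 asks sites to attempt one: "At this final follow-up visit, the subject will undergo the following assessments". The list that follows is a device assessment made up of four device reports, with no adverse-event item. The scheduled 1-month visit (CIP 8.4.4.7.1) does have one: "Evaluate the subject for ADE and SADE and submit an AE CRF- if applicable".

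**Withdrawal over device safety or performance.** The investigator "shall ask for the subject's permission to follow his/her status/condition outside of the clinical study".

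**Counting rule.** SAP 3.2, for ADE, SADE and USADE: "Subjects who die or withdraw before 1-month post-MRI scan will be included in the denominator, and their last known status of event" goes into the numerator.

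**Revisions after the scan.** If a system is revised after the scan, CIP 8.4.7.2 says "then the subject will remain in the study until the subject completes the 1 Month Post Scan visit", without exception. Table 9 in the same section has a second row for a study lead replaced by another lead, with the generator retained and non-MRI-compatible material implanted. Its action is: "The subject will be withdrawn from the study".

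**The concern.** CIP Table 2 schedules one contact after the scan visit, at 30 (+14) days. Unless an unscheduled visit takes place, the last known status of someone who leaves in between is the scan-day status. The SAP rule carries that status across the rest of the window, although 14.6 has stopped collecting the information that could change it. The subject adds one to the denominator and nothing to the event count.

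The study has no hypothesis test and no success criterion (SAP 2.2, 2.7). The descriptive percentages are the evidence submitted to the regulator, and they are reported group by group (CIP 20, SAP 2.6) with about 10 completers each. One or two subjects therefore matter to what is reported. Someone who leaves because of a device problem is also more likely than average to have a later device event, and that follow-up is placed outside the study data.

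**Working it through.** **The plan's own figure.** CIP 8.1.12 requires 10 subjects per group and allows for 5 lost: 10 + 5 = 15 per group, and 4 × 15 = 60 in total. Both figures reproduce. No power calculation exists to check (SAP 2.4).

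**What the SAP 3.2 rule does.** Let N be the subjects scanned in a group, w those who withdraw after the scan with no event recorded, and k the subjects with a recorded event.

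- SAP 3.2 percentage: k / N
- Percentage among those observed to 1 month (all k among them): k / (N − w)
- Ratio of the second to the first: N / (N − w)

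The SAP percentage is the lowest value compatible with the data. The true figure lies between k / N and (k + w) / N.

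**Assumptions.** Attrition is exactly the planned 5 per group, w of these fall after the scan, and all scanned subjects are in the denominator. Then N = 10 + w and N − w = 10. The documents do not split the 5 by time, so w is shown from 0 to 5. The zero-event column uses the exact two-sided 95% Clopper-Pearson upper bound, 1 − 0.025^(1/N); SAP 2.2.2 names this interval as optional.

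| w after scan | N | 0 events: upper bound, SAP rule | 1 event: SAP rule |
|---|---|---|---|
| 0 | 10 | 30.8% | 1/10 = 10.0% |
| 1 | 11 | 28.5% | 1/11 = 9.1% |
| 2 | 12 | 26.5% | 1/12 = 8.3% |
| 3 | 13 | 24.7% | 1/13 = 7.7% |
| 4 | 14 | 23.2% | 1/14 = 7.1% |
| 5 | 15 | 21.8% | 1/15 = 6.7% |

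Among those observed to 1 month, every row would read 0/10 (upper bound 30.8%) or 1/10 (10.0%). At w = 5 the ratio is 15/10 = 1.5. With no recorded event, the SAP rule shows 0% in every row, and its interval narrows as more subjects leave unobserved. At w = 5 and k = 0 the logical upper limit is 5/15 = 33.3%; that is a limit, not an estimate.

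**Revision passages side by side.** The 8.4.7.2 text keeps a subject with a post-scan revision in the study to the 1-month visit. Table 9 row 2 withdraws one kind of such subject. A site can follow either, and under 14.6 the choice decides whether adverse events are still recorded.

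**The case against.** The strongest reply is that the plan captures the events that matter before the subject leaves. Much of this stands.

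- ADEs and SADEs after MRI programming are reportable within 24 hours, whether or not MRI-related (CIP 16.1.2).
- The System Revision row of Table 4 requires an adverse-event evaluation, and Table 9 row 2 asks for an adverse-event form where applicable.
- SAP 3.2 keeps recorded events in the numerator.
- Vital status is collected after withdrawal.

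A reader might infer that subjects revised or explanted after the scan are counted as event-free. The documents do not support that: the event precedes the withdrawal and is reportable while surveillance is active. A reader might also see CIP 8.4.6, which says to "withdraw the subject from the study" after complete explant without replacement, as contradicting 8.4.7.2. It does not, because 8.4.7.1 defines a revision as replacement or repositioning.

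Other text helps in part. CIP 16.1 wants the subject's condition documented at each visit, and CIP 18 wants it in the source record at withdrawal. Neither is carried into the final-visit list, and neither reaches beyond the withdrawal date. CIP 16.1.2 asks for records until an event subsides, but only for an event already reported. SAP 2.9 and 3.3 summarise reasons for missing data and early termination; the visible text does not put the number observed beside the event percentage.

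It is also fair to say that many withdrawal routes come before the scan and that scan intolerance is expressly not a withdrawal (CIP 8.4.4.5). The number affected may be small.

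**Conclusion.** The point holds for one kind of subject: someone who withdraws after the scan with no event yet recorded. For that subject 14.6 and SAP 3.2 together turn unobserved time into event-free time, and the ADE, SADE and USADE percentages can only move down as a result. Under the planned attrition, the percentage among those observed would be 1.0 to 1.5 times the SAP figure, according to whether 0 or 5 of the losses per group fall after the scan. That range is an assumption.

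It would go too far to conclude that the primary safety endpoint is understated. The carry-forward rule is visible only for the ADE/SADE/USADE summary; the analysis populations (SAP 2.1) and the remaining text of SAP 2.3.1 are redacted, so nothing can be said about that denominator. Nor do the documents give any reason to expect a particular number of hidden events; an example with a missed event in a group of 10 would have to assume it.

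The mismatch between 8.4.7.2 and Table 9 row 2 is a separate wording conflict and needs reconciling in any case. Overall this is a cheap improvement that affects reported rates, not a test or a success criterion.

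**What to change.** 1. **CIP 14.6, final visit.** For any subject whose MRI settings were programmed, add an ADE/SADE evaluation with an adverse-event form to the listed assessments.
2. **CIP 14.6, after withdrawal.** With the subject's permission, record device- or MRI-related events up to 1 month after the scan in the study database, not outside it. Align the end-of-surveillance sentence in 8.3.2.
3. **CIP 8.4.7.2 and Table 9 row 2.** Reconcile them so that it is clear whether safety follow-up continues to 1 month for these subjects.
4. **SAP 3.2.** Keep the present percentage, so that events recorded before withdrawal are not lost. Beside it, give the number of subjects actually observed to 1 month and the percentage among them. Counting every unobserved subject as an event is debatable and is not needed.

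The cost is wording in both documents and a few questions, or one extra contact, for a few subjects. The final visit is already planned. The added percentage has a slightly smaller denominator and so a wider interval.
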